12.6.4.2.1 All Adverse Events

A general summary table of AEs will be presented including:

- The number of events and the number and percentage of subjects reporting at least one AE.
- The number of events and the number and percentage of subjects reporting at least one study product-related AE, broken down by product relatedness (related to THS 2.2 Menthol / mCC) and expectedness (expected for THS 2.2 Menthol / mCC).
- The number of events and the number and percentage of subjects reporting at least one AE broken down by severity including each subject only once with his worst severity.
- The number of events and the number and percentage of subjects reporting at least one SAE.
- The number of events and the number and percentage of subjects reporting at least one AE leading to any action taken, broken down by action taken related to the product (product use interrupted, product use reduced, product use stopped, not applicable, none), treatment given (yes, no), study discontinuation, other action taken.
- The number of events and the number and percentage of subjects reporting at least one AE related to study procedure

Additional summary tables of AEs will be presented with a breakdown of the number of events, as well as the number and percentage of subjects reporting each AE, categorized by SOC and PT coded according to the Medical Dictionary for Regulatory Activities (MedDRA) dictionary (version 16.0 or later).

If a subject has more than one occurrence of the same AE, the subject will be counted only once within a PT with the worst occurrence based on the presentation (e.g., for presentation by severity = most severe, for presentation by relationship = most related). Missing information on the intensity of AE will be counted as severe.

The data will be presented in the below outputs:

TFL number	Title
TABLES	
15.2.6.1.1	Summary of Adverse Events– Safety Population
15.2.6.1.2	Summary of Adverse Events– Full Safety Population
15.2.6.2.1	Summary of Adverse Events by Product Use Category in Ambulatory – Safety Population

TFL number	Title
15.2.6.2.2	Summary of Adverse Events by Product Use Category in Ambulatory – Full Safety Population
15.2.6.3.1	Summary of Adverse Events by System Organ Class and Preferred Term – Safety Population
15.2.6.3.2	Summary of Adverse Events by System Organ Class and Preferred Term – Full Safety Population
15.2.6.4.1	Summary of Adverse Events by Product Use Category, System Organ Class and Preferred Term – Safety Population
15.2.6.4.2	Summary of Adverse Events by Product Use Category, System Organ Class and Preferred Term – Full Safety Population
15.2.6.5.1	Summary of Adverse Events by System Organ Class, Preferred Term and Relationship to Study Product Exposure and Expectedness – Safety Population
15.2.6.5.2	Summary of Adverse Events by System Organ Class, Preferred Term and Relationship to Study Product Exposure and Expectedness – Full Safety Population
15.2.6.6.1	Summary of Adverse Events by Product Use Category, System Organ Class, Preferred Term and Relationship to Study Product Exposure and Expectedness – Safety Population
15.2.6.6.2	Summary of Adverse Events by Product Use Category, System Organ Class, Preferred Term and Relationship to Study Product Exposure and Expectedness – Full Safety Population
15.2.6.7.1	Summary of Adverse Events Leading to Study Product Discontinuation, Interruption, or Reduction by System Organ Class and Preferred Term – Safety Population
15.2.6.7.2	Summary of Adverse Events Leading to Study Product Discontinuation, Interruption, or Reduction by System Organ Class and Preferred Term – Full Safety Population
15.2.6.8.1	Summary of Adverse Events Leading to Study Product Discontinuation, Interruption, or Reduction by Product Use Category, System Organ Class, and Preferred Term – Safety Population
15.2.6.8.2	Summary of Adverse Events Leading to Study Product Discontinuation, Interruption, or Reduction by Product Use Category, System Organ Class, and Preferred Term – Full Safety Population
15.2.6.9.1	Summary of Adverse Events Related to Study Procedure by System Organ Class and Preferred Term – Safety Population
15.2.6.9.2	Summary of Adverse Events Related to Study Procedure by System Organ Class and Preferred Term – Full Safety Population
15.2.6.10.1	Summary of Adverse Events by System Organ Class, Preferred Term and Severity – Safety Population
15.2.6.10.2	Summary of Adverse Events by System Organ Class, Preferred Term and Severity – Full Safety Population
15.2.6.11.1	Summary of Adverse Events by Product Use Category, System Organ Class, Preferred Term and Severity – Safety Population

TFL number	Title
15.2.6.11.2	Summary of Adverse Events by Product Use Category, System Organ Class, Preferred Term and Severity – Full Safety Population
LISTINGS	
15.3.6.1.1	Listing of Adverse Events

12.6.4.2.2 Serious Adverse Events (Including Deaths)

A summary table of SAEs will be presented using the same approach as for AEs (see Section 12.6.4.2 “Adverse Events”), and including the number of events and the number and percentage of subjects reporting at least one SAE broken down by seriousness criteria (fatal, life-threatening, requires hospitalization, results in disability/incapacity, congenital anomaly/birth defect).

SAEs will also be listed in separate listings by product.

The data will be presented in the below outputs:

TFL number	Title
TABLES	
15.2.6.12.1	Summary of Serious Adverse Events by System Organ Class and Preferred Term – Safety Population
15.2.6.12.2	Summary of Serious Adverse Events by System Organ Class and Preferred Term – Full Safety Population
LISTINGS	
15.3.6.1.2	Listing of Serious Adverse Events

12.6.4.2.3 Adverse Events Leading to Discontinuation

Summaries will be presented for AEs leading to withdrawal, by product as described in Section 12.6.4.2 “Adverse Events”.

AEs leading to withdrawal will also be listed in separate listings by product.

The data will be presented in the below outputs:

TFL number	Title
TABLES	
15.2.6.13.1	Summary of Adverse Events Leading to Study Discontinuation by System Organ Class and Preferred Term – Safety Population
15.2.6.13.2	Summary of Adverse Events Leading to Study Discontinuation by System Organ Class and Preferred Term – Full Safety Population

TFL number	Title
15.2.6.14.1	Summary of Adverse Events Leading to Study Discontinuation by Product Use Category, System Organ Class and Preferred Term – Safety Population
15.2.6.14.2	Summary of Adverse Events Leading to Study Discontinuation by Product Use Category, System Organ Class and Preferred Term – Full Safety Population
LISTINGS	
15.3.6.1.3	Listing of Adverse Events Leading to Study Discontinuation

12.6.4.2.4 Laboratory Abnormalities

The shift in toxicity grades from Baseline to worst grade recorded while in the Randomized period will be presented in tables for the clinical chemistry, hematology and urinalysis parameters. Details related to the toxicity grading of laboratory abnormalities are available in Section 12.6.4.3 “Clinical laboratory Evaluation”.

The data will be presented in the below outputs:

TFL number	Title
TABLES	
15.2.6.16.1	Summary of Clinical Chemistry Parameters – Safety Population
15.2.6.16.2	Summary of Clinical Chemistry Parameters – Full Safety Population
15.2.6.17.1	Summary of Hematology Parameters – Safety Population
15.2.6.17.2	Summary of Hematology Parameters – Full Safety Population
15.2.6.18.1	Summary of Urinalysis Parameters – Safety Population
15.2.6.18.2	Summary of Urinalysis Parameters – Full Safety Population

12.6.4.2.5 THS 2.2 Device Events

All events relating to the device type will be listed for each subject, including event description, device type the event relates to, severity of event, AE relationship, proposed solution and onset/stop dates/times. Device events will be classified according to PMI device controlled terminology .

A summary table of device events will be presented by product, including:

- Number of device events and the number and percentage of subjects reporting at least one device event.
- Number of device events and the number and percentage of subjects categorized by severity of device event (minor, major)
- Number of device events and the number and percentage of subjects categorized by AE relationship (related, not related)
- Number of device events and the number and percentage of subjects categorized by event description.

Device events and inventory will be listed by product.

The data will be presented in the below outputs:

TFL number	Title
TABLES	
15.2.6.15.1	Summary of THS 2.2 Menthol Device Events – Safety Population
15.2.6.15.2	Summary of THS 2.2 Menthol Device Events – Full Safety Population
LISTINGS	
15.3.6.2	Listing of THS 2.2 Menthol Device Events and Malfunctions

12.6.4.3 Clinical Laboratory Evaluation

Table 22 below lists the hematology, clinical chemistry and urine analysis parameters to be assessed in this study.

Table 22: List of Laboratory Safety Parameters

Hematology	Clinical chemistry	Urine analysis
Hematocrit	Albumin	pH
Hemoglobin	Total protein	Bilirubin
Mean corpuscular hemoglobin	Alkaline phosphatase	Glucose
Mean corpuscular hemoglobin concentration	Alanine aminotransferase	Nitrite
Mean corpuscular volume	Aspartate aminotransferase	Red blood cell traces
Platelet count	Blood urea nitrogen	Protein
Red blood cell count	Creatinine	Specific gravity
WBC count	Gamma-glutamyltransferase	
Differential WBC count:	Fasting glucose	
• Neutrophils	Lactate dehydrogenase	
• Basophils	Potassium	
• Eosinophils	Sodium	
• Lymphocytes	Total bilirubin	
• Monocytes	Direct bilirubin	
	Total cholesterol	
	Triglycerides	

Any clinical safety laboratory test result that is outside of the normal reference range will be reviewed by the principal investigator (PI) and assessed for clinical relevance. If the PI considers the abnormal result to be of clinical relevance, then it must be recorded as a concomitant disease at Screening, or if not present at Screening, as an AE during the study. If the condition worsens from screening to after product-use it will be recorded as an AE.

The grading scheme used in the Common Terminology Criteria for Adverse Events and Common Toxicity Criteria [CTCAE] version 4.03) will be used by the PI to assess abnormal laboratory values. These CTCAE grades will be derived programmatically in the creation of the datasets.

Laboratory data will be summarized and listed at Screening and Day 0 for the Pre-Randomization period; and at Baseline, Day of Discharge (Day 6), Day 30 Visit, Day 60 Visit and Day 90 Visit for the Randomized period data together with changes from Baseline. The number and percentage of subjects with normal results, high/low results and abnormal clinical significant result (as defined by PI comment), and CTCAE toxicity grading will be tabulated for laboratory parameters, together with shift in normality (Normal, Abnormal NCS, Abnormal CS) and in CTCAE toxicity grading from Baseline.

Listings for the clinical laboratory data will include the following information: change from Baseline, normal/ high/low (with respect to the reference range), abnormal clinically significant (as defined by the PI comments) and shift from Baseline, the PI comments, the CTCAE grade and the shift in CTCAE grade. Only CTCAE grades greater than zero will be presented.

The data will be presented in the below outputs:

TFL number	Title
TABLES	
15.2.6.16.1	Summary of Clinical Chemistry Parameters – Safety Population
15.2.6.16.2	Summary of Clinical Chemistry Parameters – Full Safety Population
15.2.6.17.1	Summary of Hematology Parameters – Safety Population
15.2.6.17.2	Summary of Hematology Parameters – Full Safety Population
15.2.6.18.1	Summary of Urinalysis Parameters – Safety Population
15.2.6.18.2	Summary of Urinalysis Parameters – Full Safety Population
LISTINGS	
15.3.6.4	Listing of Clinical Chemistry Data, Shift, Changes from Baseline and CTCAE grades
15.3.6.5	Listing of Hematology Data Shift, Changes from Baseline and CTCAE grades
15.3.6.6	Listing of Urinalysis Data Shift, Changes from Baseline and CTCAE grades

12.6.4.4 Vital Signs, Physical Findings and Other Observations Related to Safety

12.6.4.4.1 Prior and Concomitant Medication

Prior medication is defined as any medication that started and ended prior to Screening. Concomitant medication is defined as any medication starting on or after Screening. Medications that started prior to Screening and are ongoing at Screening are considered as concomitant.

All medications will be listed by product using PT and Anatomical Therapeutic and Chemical (ATC) codes (World Health Organization-Drug Dictionary Enhanced

[WHO-DDE] Q1 2012). A flag will be presented on the listing indicating whether the medication is prior or concomitant. Prior and concomitant medications will be listed by randomization arm.. Prior and Concomitant medications will be summarized by randomization arm for the Safety population showing the number and percent of subjects who used the medication at least once by ATC 1st and 2nd levels and preferred drug name.

The data will be presented in the below outputs:

TFL number	Title
TABLES	
15.2.6.19.1	Summary of Prior Medication by Anatomical Therapeutic Classes (ATC) 1 and 2 – Safety Population
15.2.6.19.2	Summary of Prior Medication by Preferred Drug Name – Safety Population
15.2.6.20.1	Summary of Concomitant Medication by Anatomical Therapeutic Classes (ATC) 1 and 2 – Safety Population
15.2.6.20.2	Summary of Concomitant Medication by Preferred Drug Name – Safety Population
LISTINGS	
15.3.6.3	Listing of Prior and Concomitant Medication

12.6.4.4.2 Physical Examination

Physical examination data recorded at the Screening visit, Admission (Day -2), Day of discharge (Day 6), Day 30 Visit, Day 60 Visit and Day 90 Visit will be listed by product. Subject's data with abnormal and abnormal clinically significant physical examination findings will be flagged. The number of subjects and percent with normal, abnormal and abnormal clinically significant results will be tabulated by body systems for the Randomized period at Baseline, day of discharge, Day 30 Visit, Day 60 Visit, and Day 90 Visit, including shifts in normality from Baseline.

Body weight and waist circumference recorded at Admission (Day -2), Day of discharge from Confinement (Day 6), Day 30 Visit, Day 60 Visit and Day 90 Visit; and body height recorded at the Screening visit will also be listed together with BMI. Descriptive statistics of body weight, waist circumference, body height and BMI (BMI will also be categorized as shown in Section 7.5 "Categorical Variables"), at Baseline and Day of discharge and Day 90 Visit will be presented for the Safety population.

Summaries will be presented for the Safety population by study arm

The data will be presented in the below outputs:

TFL number	Title
TABLES	
15.2.6.24	Summary of Physical Examination of Body Systems – Safety Population
15.2.6.25	Summary of Weight, Waist Circumference and BMI Results – Safety Population
LISTINGS	
15.3.6.10	Listing of Physical Examination Findings, Shift and Changes from Baseline

12.6.4.4.3 Vital Signs

Systolic and diastolic blood pressure, pulse rate and respiratory rate measured during the study will be listed by study visit, including low/normal/high results.

Descriptive statistics will be presented for supine systolic and supine diastolic blood pressure, pulse rate and respiratory rate at Baseline, and on every subsequent day of both the confinement and ambulatory periods by product for each study day. Vital signs data will be summarized together with changes from Baseline.

The data will be presented in the below outputs:

TFL number	Title
TABLES	
15.2.6.21	Summary of Supine Vital Signs – Safety Population
LISTINGS	
15.3.6.7	Listing of Vital Signs Data and Changes from Baseline

12.6.4.4.4 Spirometry

Spirometry parameters assessed during the study include:

- Measured forced expiratory volume in 1 second (FEV₁)
- Measured forced vital capacity (FVC)
- FEV₁/FVC
- Predicted FEV₁
- Percent of predicted FEV₁ (% pred)
- Predicted FVC
- Percent of predicted FVC (% pred)
- Measurement interpretation (categories: normal, abnormal, abnormal clinically significant)

The above data are collected at Screening, Day 0, Day of Discharge (Day 6), and Day 90 Visit. At Screening, data are collected prior and post-bronchodilator, also including the brand (trade) name and dose of the bronchodilator. All other spirometry assessments are performed without bronchodilator.

Spirometry predicted values will be standardized to the predicted set from the Japanese Respiratory Society. Spirometry data values and normality evaluation will be listed by sequence and study day. Assessments performed after Baseline will be listed together with change from Baseline and shift in normality. Spirometry data from subjects who had significant clinical findings will be highlighted in listings.

Descriptive statistics will be presented for FEV₁(L), FEV₁ (% pred), FVC(L), FVC(% pred), and FEV₁/FVC at Baseline (pre or without bronchodilator), Day of Discharge (Day 6), and Day 90 Visit by study arm, and overall for the Safety population in the Randomized period. Spirometry data will be summarized together with changes from baseline, and the number and percentage of subjects with normal/abnormal non clinically significant/abnormal clinically significant results. Data with and without bronchodilator at Screening will be summarized together with the spirometry data at Day 0 for the Safety population in the Pre-randomization period.

The data will be presented in the below outputs:

TFL number	Title
TABLES	
15.2.6.23	Summary of Spirometry Results – Safety Population
LISTINGS	
15.3.6.8	Listing of Spirometry Data and Changes from Baseline

12.6.4.4.5 Electrocardiogram

The ECG data will be obtained directly from the 12-lead ECG traces, i.e. not centrally read. These data include the PR, QT, and QTcB intervals; QRS duration; and heart rate; and normality evaluation (normal, abnormal non-clinically significant, clinically significant, together with any PMI comments to the abnormality). In addition the QTcF value will be presented.

ECG data values and normality evaluations will be listed by product and study day (Screening, Day 6, Day 30 Visit, Day 60 Visit and Day 90 Visit) together with changes from baseline and shift in normality. ECG data from subjects which had significant clinical findings will be highlighted in listings.

Descriptive statistics will be presented for ECG data at Baseline, and Day 6, Day 30 Visit, Day 60 Visit and Day 90 Visit by study arm. ECG data will be summarized together with changes from Baseline, and the number and percentage of subjects with normal/abnormal non clinically significant/abnormal clinically significant results.

The data will be presented in the below outputs:

TFL number	Title
TABLES	
15.2.6.22	Summary of ECG Results – Safety Population

TFL number Title

LISTINGS

15.3.6.9 Listing of ECG Data and Changes from Baseline

12.6.4.4.6 Assessment of Cough

Cough questionnaire is assessed on a daily basis from Day 0 to Day 6 and Day 30 Visit, Day 60 Visit and Day 90 Visit. Questionnaire details are reported in Section 7.3.7 “Cough Assessment”.

The number and percentage of subjects reporting a cough will be summarized by randomization arm and presented for the day prior to the assessment. The responses to the individual items, including the VAS evaluating the level of cough bother and 3 Likert scales measuring the intensity, the frequency of cough and the amount of sputum production will be listed and summarized on each day by randomization arm, for all subjects who filled in the questionnaire. The answers to the open question related to any other important observation will be listed.

The data will be presented in the below outputs:

TFL number Title

TABLES

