7.8.3.2 Assessment of Cough

Subjects will be asked to assess the respiratory symptom 'cough' on a VAS, on three Likert scales, and with an open question on a daily basis during the confinement period (from Day 0 to Day 6), and at every visit on Day 30 Visit (Day 31), Day 60 Visit (Day 61) and Day 90 Visit (Day 91). From Day 0 to Day 6 only, assessment of cough must be done prior to start of product use/smoking and no later than 10:00 AM. On Day 30 Visit and Day 60 Visit, assessment of cough will be conducted irrespective of the time of product use but no later than 10:00 AM. On Day 90 Visit (Day 91), assessment of cough will be conducted prior to smoking but no later than 10:00 AM.

Subjects will be asked if they have experienced a regular need to cough, e.g. whether they have coughed several times in the previous 24 hours prior to assessment. If the answer is 'yes', subjects will be asked to complete a VAS, three Likert scales, and to answer the open question.

On the VAS, subjects will assess how bothersome their cough was during the previous 24 hours. The VAS ranges from 'not bothering me at all' to 'extremely bothersome.'

Furthermore, subjects will assess the intensity and frequency of cough and the amount of sputum production during the previous 24 hours on Likert scales.

The intensity of cough will be assessed on a 5-point Likert scale ranging from 1 to 5, with 1 = very mild – 2 = mild – 3 = moderate – 4 = severe – 5 = very severe.

The frequency of cough will be assessed on a 5-point Likert scale ranging from 1 to 5, with 1 = rarely – 2 = sometimes – 3 = fairly often – 4 = often - 5 = almost always.

The amount of sputum production will be assessed on a 4-point Likert scale ranging from 0 to 3, with 0 = no sputum – 1 = a moderate amount of sputum – 2 = a larger amount of sputum – 3 = a very large amount of sputum.

Finally, subjects will be asked with an open question if they want to share any other important observations with the study collaborators about their coughing.

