12.6.5 Safety Analysis

In general, all safety data will be listed and tabulated on the safety population by product arm, using the approach described in Section 12.1.3. Safety variables collected during exposure periods will also be reported by product exposure.

Adverse events data will serve as the primary assessment of safety. Other safety variables monitored in this study include: respiratory symptoms (cough assessment VAS and Likert scales); vital signs (systolic and diastolic blood pressure, pulse rate, respiratory rate); spirometry; electrocardiogram (ECG) data; clinical chemistry, hematology, concomitant medications, and urine analysis safety panel; physical examination.

The number and percentage of subjects with AEs and SAEs will be tabulated by system organ class (SOC) and preferred term (PT), summarized for the safety population and the full safety population. Summaries will also be presented for AEs leading to withdrawal, AEs leading to Death, AEs by relatedness to product exposure, AEs by severity, and laboratory AEs. Tabulations will be performed for both the number of subjects experiencing an event and the number of events.

The number and percentage of subjects with clinical findings by sequence for laboratory parameters will be summarized for the safety population and the full safety population. Shift tables showing change from baseline of clinical findings will be provided for: ECGs, physical examinations and laboratory parameters (both shifts in normal ranges and toxicity grades). Descriptive statistics will be summarized by visit and change from baseline for laboratory parameters, ECG, respiratory symptoms, and vital signs.

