7.3.7 Cough Assessment

Subjects will be asked to assess the respiratory symptom 'cough' on a VAS, on three Likert scales, and with one open ended question on a daily basis during the confinement period (from Day 0 to Day 6), and on the second day of each ambulatory period visit (Day 30 Visit, Day 60 Visit and Day 90 Visit). From Day 0 to Day 6, assessment of cough is done prior to start of product use/smoking and no later than 10:00 AM. On Day 31, Day 61 assessment of cough will be conducted irrespective of the start of product

use and not later than 10:00 AM. On Day 91 the assessment of cough will be conducted prior to smoking/product use but no later than 10:00 AM.

Subjects will be asked if they have experienced a regular need to cough, e.g., whether they have coughed several times in the previous 24 hours prior to assessment. If the answer is 'yes', subjects will be asked to complete questionnaire.

The VAS will assess how bothersome cough is to the subject ranging from 'not bothering me at all' to 'extremely bothersome', and this will be given a numeric value between 0 and 100, measured on a 100mm scale.

Subjects will also be asked to assess the intensity and frequency of cough and the amount of sputum production on Likert scales as presented in Table 7.

Table 7 : Cough Assessment Likert Scales

Question	Likert Scale
1 The intensity of cough	1 = very mild 2 = mild 3 = moderate 4 = severe 5 = very severe
2 The frequency of cough	1 = rarely 2 = sometimes 3 = fairly often 4 = often 5 = almost always
3 The amount of sputum production	0 = no sputum 1 = a moderate amount of sputum; 2 = a larger amount of sputum; 3 = a very large amount of sputum.

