12.1.5.1 Insufficient Data for Analysis/Presentation

If there are no values or events at the general value then the break out should not be presented. For example if the number of AEs related to study procedure is zero then the presentation by severity of related events will not be produced.

Some of the TFLs may not have sufficient numbers of subjects or data for presentation. If this occurs, the blank TFL shell will be presented with a message printed in the center of the table, such as, "No serious adverse events occurred for this study."

For categories of continuous data summaries that have <4 subjects no summaries will be shown.

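### Cough severity is summarised only among subjects reporting regular cough, so the by-arm tables do not compare the randomised arms, and the protocol's change from baseline is dropped

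*SAP*

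**What the plan says.** - **Who answers.** Protocol 7.8.3.2 opens the assessment with a yes/no item on regular need to cough over the previous 24 hours. It continues: "If the answer is 'yes', subjects will be asked to complete a VAS, three Likert scales, and to answer the open question". SAP 7.3.7 has the same rule: "If the answer is 'yes', subjects will be asked to complete questionnaire".
- **The scales.** For the VAS, "this will be given a numeric value between 0 and 100, measured on a 100mm scale". For intensity, "The intensity of cough will be assessed on a 5-point Likert scale ranging from 1 to 5"; it starts at very mild and has no level for absent cough. Neither document gives a value to a subject who answers 'no'. The questionnaire imputation rule in SAP 12.1.5 covers MNWS, QSU-brief and MCEQ only.
- **What is tabulated.** In SAP 12.6.4.4.6, "The number and percentage of subjects reporting a cough will be summarized by randomization arm and presented for the day prior to the assessment". The individual items "will be listed and summarized on each day by randomization arm, for all subjects who filled in the questionnaire". Both are on the Safety Population, with no test.
- **Change from baseline.** Protocol 12.6.5: "Descriptive statistics will be summarized by visit and change from baseline for laboratory parameters, ECG, respiratory symptoms, and vital signs". SAP 12.6.4.3, 12.6.4.4.3 and 12.6.4.4.5 carry this through for laboratory data, vital signs and ECG. SAP 12.6.4.4.6 does not do so for cough, and SAP Section 9 does not record the omission.
- **Small cells.** SAP 12.1.5.1: "For categories of continuous data summaries that have <4 subjects no summaries will be shown".

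**The concern.** Whether a subject reports regular cough on a given day is itself an outcome that the assigned product or abstinence may change. A severity mean restricted to those subjects compares different subsets in each arm and on each day, so randomisation no longer protects the comparison. A product that induces new mild cough adds low scores and pulls the mean down. One that clears mild cough removes low scores and pushes it up.

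The table carries some weight for safety. Cough is the only symptom named under the respiratory-symptom endpoint. Protocol 7.8.3 also says that symptoms captured on the questionnaires or the VAS need not be recorded as adverse events, because those data will be analysed in the final report; recording them is left to the investigator. Worsening cough may therefore appear mainly in these tables. A change score would not repair this as things stand, since it would exist only for subjects coughing at both times.

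**Working it through.** The documents state no cough rate, VAS distribution or precision target, so there is no figure of the plan's own to reproduce. The check is arithmetic on assumed values.

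**Inputs.** Arm size 80 (planned THS 2.2 Menthol arm, SAP Section 8). Assumed: 40% cough at baseline, so 32 subjects, 16 with VAS 10 and 16 with VAS 40. Nobody's own score changes; subjects only start or stop coughing. Non-coughers count as 0 in the all-subject mean.

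**Formulas.** Mean among coughers = sum of VAS / number coughing. All-subject mean = the same sum / 80.

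| Scenario | Coughing | Sum of VAS | Mean among coughers | All-subject mean |
|---|---|---|---|---|
| Baseline | 32 (40%) | 16×10 + 16×40 = 800 | 800/32 = 25.0 | 800/80 = 10.0 |
| Half of mild coughs resolve | 24 (30%) | 8×10 + 16×40 = 720 | 720/24 = 30.0 | 720/80 = 9.0 |
| All mild coughs resolve | 16 (20%) | 16×40 = 640 | 640/16 = 40.0 | 640/80 = 8.0 |
| 16 new mild coughs | 48 (60%) | 32×10 + 16×40 = 960 | 960/48 = 20.0 | 960/80 = 12.0 |

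In every changed row the two means move in opposite directions.

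**Sensitivity to prevalence.** At 20% baseline cough (8 at VAS 10, 8 at VAS 40), the mean among coughers again goes from 400/16 = 25.0 to 320/8 = 40.0 when all mild coughs resolve. The all-subject mean goes from 400/80 = 5.0 to 320/80 = 4.0.

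**When it does not happen.** If half of the mild and half of the more bothersome coughs resolve, the mean among coughers is (8×10 + 8×40)/16 = 25.0, unchanged, while the all-subject mean halves to 400/80 = 5.0. Opposite movement needs entry to or exit from coughing to depend on severity.

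**Change from baseline.** In the last two table rows, every subject with a VAS at both times (16 and 32 respectively) has change 0. The all-subject change is 8.0 − 10.0 = −2.0 in one and 12.0 − 10.0 = +2.0 in the other. A change score limited to coughers at both times would not distinguish them.

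**Small cells.** In an arm of 40, 3 or fewer coughers (3/40 = 7.5%) would leave that day's VAS summary blank, if the fewer-than-4 rule is applied to this table.

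**The case against.** Much of the missing context is already planned. The same SAP section tabulates the number and percentage coughing by arm, and SAP 12.1.3 puts n beside every continuous summary. A reader who sees the mean rise from 25 to 40 would also see n fall from 32 to 16. If the Likert items are tabulated as categorical data under SAP 12.1.3, their counts show which severity levels emptied. Frequency plus severity given occurrence is a recognised presentation. This stands: the denominator shift is visible to a careful reader. It does not supply a severity table on the randomised denominator or restore the change from baseline.

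MNWS item 12 asks every arm about coughing on a 0 to 4 scale with 0 as none, on the same days. But SAP 7.3.5 leaves it out of the total score, and SAP 12.6.3.1.4 only lists individual answers, so it fills no planned table.

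Scoring 'no' as VAS 0 can also be disputed. 'No' means no regular need to cough, so it may include occasional cough with some bother, and it would be merged with regular cough rated as not bothersome. This also stands, and the score should be labelled a convention.

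A reader might infer that VAS data disappear on days with few coughers. They do not: the small-cell rule concerns continuous summaries, and individual responses stay in listing 15.3.6.15. Finally, the table shells are in a separate document and might show more, but the SAP text does not call for it.

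**Conclusion.** The point holds for a descriptive safety table. The cough severity summaries by arm and day are conditioned on a post-randomisation outcome, do not compare the randomised arms, and can move opposite to total burden. No planned table shows severity over all subjects assessed. Separately, the SAP departs from Protocol 12.6.5 on change from baseline for respiratory symptoms and does not declare it.

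The possible reversal follows from the design of the summary; its size does not come from the documents. The figures above rest on assumed prevalence, an assumed VAS split and severity-dependent onset or resolution, none of which the documents address.

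A reader might go further and infer that THS 2.2 Menthol or abstinence will look worse, or better, than it is. The documents do not support a direction: nothing in them says which coughs would start or resolve in which arm, and if resolution is unrelated to severity the mean among coughers is unchanged on average. Nor is any trial conclusion at risk. Cough has no test or success criterion, adverse events are the primary safety assessment, and the primary biomarker analysis is untouched. The consequence is a safety table that is easy to misread.

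**What to change.** In SAP 7.3.7 and 12.6.4.4.6:

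1. Use all subjects assessed that day as the denominator, and add a 'no regular cough' category to the intensity, frequency and sputum tables. Keep it distinct from the existing no-sputum level.
2. Add a VAS summary over all assessed subjects with 'no' scored 0, stated to be a convention, showing the median, quartiles and percentage above zero alongside the mean.
3. Add the change from baseline that Protocol 12.6.5 specifies, or a shift table that includes the 'no regular cough' category. If it is left out deliberately, list that in SAP Section 9.
4. Leave an unanswered yes/no item, or a 'yes' with blank items, as missing rather than 0.
5. Keep the coughers-only table as supplementary, with n/N shown.

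The cost is SAP wording, a derivation from the yes/no item already collected, and a few table rows. The drawbacks are a VAS distribution with many zeros and a 'no' group that may include occasional, non-regular cough.
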